THE UNIVERSITY OF TEXAS

Protocol Abstract Page

Randomized controlled study of post-transplant azacitidine for prevention of acute myelogenous leukemia and myelodysplastic syndrome relapse
(VZ-AML-PI-0129)
2008-0503

Core Protocol Information

Study Chairman:	[name]
Department:	Stem Cell Transplantation and Cellular Therapy
[contact]
Unit:	423
Full Title:	Randomized controlled study of post-transplant azacitidine for prevention of acute myelogenous leukemia and myelodysplastic syndrome relapse (VZ-AML-PI-0129)
Protocol Phase:	Phase III
Version Status:	Terminated 08/20/2018
Version:	29
Document Status:	Final

Abstract

Objectives:

Primary

1. To compare in a randomized controlled fashion the relapse-free survival of acute myelogenous leukemia and myelodysplastic patients treated with post transplant maintenance azacitidine.

Secondary

1. To compare survival of patients receiving azacitidine with that of untreated controls.
2. To document toxicity of maintenance therapy with azacitidine.

Rationale: (Be as concise as possible)

Allogeneic hematopoietic stem cell transplantation for patients with high-risk acute myelogenous leukemia (AML) and myelodysplastic syndrome (MDS) is associated with high failure rates. Although this form of treatment is associated with a high complete remission rate, the major cause of failure is disease relapse, which usually occurs early after transplantation.

Here we propose to use maintenance treatment with low doses of 5-azacitidine (Vidaza) after transplantation. The rationale for the choice of low doses of azacitidine is as follows: recovering marrows after transplantation are very susceptible to myelosuppression, and higher doses are not well tolerated; in addition, we are not seeking a cytotoxic effect, but hope to induce hypomethylation and myeloid cell differentiation and possibly, magnify the graft-versus-leukemia effect. We have defined the safety of a dose at 32 mg/m² for 5 days, repeated at 28 day cycles, and now plan to evaluate this maintenance strategy in a randomized, controlled fashion.

Eligibility: (List All Criteria)

Inclusion:

- 1) Patients with a diagnosis of AML (World Health Organization classification: >=20% blasts in the bone marrow and / or peripheral blood) or MDS (International Prognostic Scoring System intermediate-1 or higher) that at the time of allogeneic transplantation were in: - Induction Failure, relapsed disease or second or greater remission; patients in first complete remission that required more than 1 cycle of treatment to achieve the remission, or that have AML evolving from MDS, or that had the following abnormalities: FLT3 mutation, deletion of chromosome 5 or 7, MLL gene rearrangement, or more than or equal to 3 cytogenetics abnormalities. Patients with de novo or therapy-related MDS, CMML, or AML are also eligible, regardless of cytogenetics or molecular rearrangements.
- 2) Biphenotypic Leukemia that at the time of allogeneic transplantation was in induction failure, relapsed disease, first, second or greater remission.
- 3) Patients must be in complete remission post transplant.
- 4) Patient may be enrolled 40 to 100 days after transplant.
- 5) Age 18 to 75 years old.
- 6) Serum creatinine < 1.8 mg/dL or creatinine clearance greater or equal than 40 cc/min as defined by the Cockcroft-Gault Equation*. a. Males(mL/min):(140-age)*IBW(kg) / 72*(serum creatinine(mg/dl)) b. Females(mL/min):0.85*(140-age)*IBW(kg) / 72*(serum creatinine(mg/dl)).
- 7) Serum direct bilirubin < 1.5 mg/dL (unless Gilbert's syndrome).
- 8) SGPT <= 200 IU/ml unless related to patient's malignancy.
- 9) Be able to understand and sign informed consent.

Exclusion:

- 1) Active uncontrolled infection.
- 2) Presence of uncontrolled graft-versus-host disease.

- 3) Patients that underwent allogeneic transplantation as a treatment of graft failure.
- 4) Pregnancy or breast-feeding (women of childbearing potential, any female who has experienced menarche and who has not undergone surgical sterilization or is not post-menopausal with a positive serum pregnancy test).
- 5) Known or suspected hypersensitivity to azacitidine or mannitol.
- 6) Patients with advanced malignant hepatic tumors.

Is there an age limit? Yes

Why? Provide scientific justification:

The upper limit (75 years) is determined by physiologic limitations. The lower limit is dictated by the small numbers of patients that have the diseases studied here, a fact that prevents meaningful conclusions in the pediatric population.

Disease Group:

Leukemia

Treatment Agents/Devices/Interventions:

Azacitidine

Proposed Treatment/Study Plan:

Standard treatment post allogeneic transplant is supportive care only.

Statistical Considerations:

Preliminaries

This is a randomized, controlled phase III trial to compare azacitidine (AZA) maintenance to standard of care in patients with high risk AML/MDS who have undergone an allogeneic stem cell transplant (allotx). Patients will be randomized fairly between azacitidine and standard of care. Starting at 40 to 100 days post allotx, patients randomized to the azacitidine arm will receive 32 mg/m² for five consecutive days of each 28 day cycle and the maximum treatment will be 12 cycles. Each cycle will consist of approximately 28 days, allowing the possibility that treatment within a cycle may be delayed for up to 4 weeks due to organ toxicity or hematologic toxicity.

Group sequential design

The primary outcome for treatment evaluation will be relapse-free survival (RFS) time. A null historical RFS time of 6 months will be assumed. The goal will be to

test the hypothesis that azacitidine provides at least a 50% improvement in $m =$ median RFS, from 6 to 9 months. An accrual rate of 6 patients per month will be assumed. A two-sided group sequential procedure will be used [2] with overall type I error .05 and power .80 to detect the alternative $m = 9$ months, with up to 2 interim tests and one final test, including both outer bounds for superiority and inner bounds for futility. All tests will be based on a standardized log rank statistic, and will be performed using the following cut-offs.

No. Events	Outer Z-score cut-off to reject the null hypothesis (Superiority)	Inner Z-score cut-off to accept the null hypothesis (Futility)
71	+/- 3.7103	+/- .2438
142	+/- 2.5114	+/- 1.0268
214	+/- 1.993	+/- 1.993

The number of patients accrued (sample size) required to achieve the necessary numbers of events required by the group sequential tests will be between 213 and 246 (all to be enrolled at MDACC).

The randomization will be stratified by disease (AML, MDS, biphenotypic leukemia).

Secondary outcomes

Additional outcomes that will be recorded and analyzed will include overall survival (OS) time, acute (grade 3 or 4) graft-versus host disease, organ toxicity and hematologic toxicity.

Data analyses

All adverse events will be cross-tabulated with treatment arm, and the rates compared using a Fisher exact test. Unadjusted RFS and OS times will be estimated using the Kaplan-Meier method. Covariate adjusted comparisons will be done using a Cox model or other appropriate time-to-event regression model to be determined by preliminary goodness-of-fit analyses.

Where Will Participants Be Enrolled:

Only at MDACC

Is this an NCI-Cancer Therapy Evaluation Protocol (CTEP)? No

Is this an NCI-Division of Cancer Prevention Protocol (DCP)? No

Estimated Accrual:

Total Accrual at MDACC: 246
Estimated monthly accrual at MDACC: 6

Accrual Comments:

Do you expect your target population to include non-english speaking participants? No

Location of Treatment:

This protocol is performed on an Outpatient basis.

Length of Stay: What is the length & frequency of hospitalization?

No hospitalization is planned under this study.

Return Visits: How often must participants come to MDACC?

Daily for 5 days of each 28 day-cycle (for drug administration). Once prior to starting the drug and once weekly for 2 weeks after drug administration is completed for labs. Pts are to receive azacitidine for no more than 1 year after the first dose.

Home Care: Specify what, if any, treatment may be given at home.

There is no home care under this study. However, local physicians, should they agree to administer the drug as prescribed here, will administer azacitidine.

Name of Person at MDACC Responsible for Data Management: [name]

Prior protocol at M. D. Anderson:

Has the Principal Investigator ever had a clinical or behavioral protocol at MDACC that accrued patients?
Yes

Data Monitoring Committee:

Is treatment assignment randomized? Yes

Is this a blinded or double-blinded study? No

Does this Protocol need data safety monitoring? Yes

Provide the name of the data safety monitoring board (DSMB) monitoring this protocol:
MDACC DMC

Does this protocol have a schedule for interim and final analysis? Yes

Please describe:

We plan to have interim analyses when accrual reaches 71 and 142 patients, and a final analysis when we complete enrollment, as described in the statistical section.

Radiation Safety:

Does this study involve the administration of radioisotopes or a radioisotope labeled agent?	No
Is the radioactive compound (or drug) FDA approved and/or commercially available?	No

Investigational New Drugs:

Does this protocol require an IND? No

Please confirm that the protocol meets all criteria for exemption according to 21CFR 312.2(b), noted below:

(b) Exemptions. (1) The clinical investigation of a drug product that is lawfully marketed in the United States is exempt from the requirements of this part if all the following apply:

- (i) The investigation is not intended to be reported to FDA as a well-controlled study in support of a new indication for use nor intended to be used to support any other significant change in the labeling for the drug;
- (ii) If the drug that is undergoing investigation is lawfully marketed as a prescription drug product, the investigation is not intended to support a significant change in the advertising for the product;
- (iii) The investigation does not involve a route of administration or dosage level or use in a patient population or other factor that significantly increases the risks (or decreases the acceptability of the risks) associated with the use of the drug product;
- (iv) The investigation is conducted in compliance with the requirements for institutional review set forth in part 56 and with the requirements for informed consent set forth in part 50; and
- (v) The investigation is conducted in compliance with the requirements of 312.7.

Rationale for Exemption:

Please include a detailed rationale as to why this drug should be considered exempt from FDA IND regulations, including any available references to the prior use of the regimen or drug combination in human subjects.

We are completing study 2005-0417, which determined the dose and schedule of azacitidine given after allogeneic transplant. That protocol did not require an IND. Here we plan to determine the efficacy of this approach, using the dose determined in the previous study, and therefore believe that we do not need an IND.

If this protocol includes an FDA Approved Therapy, please list the disease, dose and route of administration:

	Approved Use	Proposed in this Protocol
Disease:	MDS	AML/MDS
Dose:	75 mg/m ² X 7 days	32 mg/m ² X 5 days
Route of Administration:	SQ	SQ

Investigational Device:

Is the Investigational Device approved by the FDA? N/A

Is the Investigational Device being used in the manner approved by the FDA? N/A

Has the Investigational Device been modified in a manner not approved by the FDA? N/A

Name of Device:

Manufacturer:

What is the FDA Status of the Investigational Device?

Is the study being conducted under an Investigational Device Exemption (IDE)? No

IDE Holder:

IDE Number:

Risk Assessment:

Please answer the following questions regarding the Investigational Device.

Intended as an implant? No

Purported or represented to be for use supporting or sustaining human life? No

For use of substantial importance in diagnosing, curing, mitigating, or treating disease, or otherwise preventing impairment of human health? No

You may attach sponsor documentation of the risk assessment:

Will participant be charged for the Investigational Device?

Sponsorship and Support Information:

Does the Study have a Sponsor or Supporter? Yes

Sponsor or Supporter: Celgene

Type(s) of Support: Agent

Monitored by Sponsor or Sponsor Representative (CRO)? No

Is this Protocol listed on any Federal Grant or Foundation Funding Application? No

Biosafety:

Does this study involve the use of Recombinant DNA Technology? No

Does this study involve the use of organisms that are infectious to humans? No

Does this study involve stem cells? No

Technology Commercialization:

Does this study include any agents or devices manufactured or produced at No
MD Anderson Cancer Center?

Laboratory Tests:

Where will laboratory tests be performed on patient materials? (Please select all that apply)

Other

Please provide the name of the test(s), the purpose of the test, and the performing laboratory identification and contact information.

[name] laboratory and [name] laboratory at MD Anderson will receive samples to study immune recovery after allogeneic transplant. [name] laboratory and [name] laboratory at MD Anderson will receive samples for methylation studies.

Manufacturing:

Will you manufacture in full or in part (split manufacturing) a drug or biological product at the M. D. Anderson Cancer Center for the proposed clinical study? No

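### The last sentence of inclusion 1 appears to admit first-remission AML without any listed high-risk feature, in conflict with the high-risk population of the statistical section, and neither the strata nor the primary test allows for the resulting mix of risk

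*Combined protocol and SAP*

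**What the plan says.** **Eligibility, inclusion 1.** AML or MDS qualifies by status at transplant: induction failure, relapse, or second or later remission. First remission qualifies only with an adverse feature: "patients in first complete remission that required more than 1 cycle of treatment to achieve the remission, or that have AML evolving from MDS", or one of "FLT3 mutation, deletion of chromosome 5 or 7, MLL gene rearrangement, or more than or equal to 3 cytogenetics abnormalities". MDS carries its own floor, "MDS (International Prognostic Scoring System intermediate-1 or higher". The criterion then ends: "Patients with de novo or therapy-related MDS, CMML, or AML are also eligible, regardless of cytogenetics or molecular rearrangements".

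**Statistical Considerations, Preliminaries.** The trial is described as being in "patients with high risk AML/MDS who have undergone an allogeneic stem cell transplant". The Rationale on the abstract page also speaks of high-risk disease.

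**Statistical Considerations, Group sequential design.** "A null historical RFS time of 6 months will be assumed". No source cohort is given. The design targets a median of 9 months, with log-rank tests at 71, 142 and 214 events, 213 to 246 patients and accrual of 6 per month. Nothing says that the log-rank statistic is stratified. On allocation: "The randomization will be stratified by disease (AML, MDS, biphenotypic leukemia"; CMML is not in that list, and there is no factor for risk or remission status.

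**Data analyses.** Covariate-adjusted comparisons by a Cox or similar model are planned, but no covariate is named.

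**The concern.** The first part of inclusion 1 selects first-remission AML by risk. The last sentence admits AML by origin and sets genetics aside. The two parts describe different populations, and two screeners could decide differently on the same patient.

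Three things are at stake. The result might not describe the high-risk population that the plan names. If the 6-month figure came from high-risk patients, a wider intake would lengthen the control median and delay the 214th event. And mixing patients of different prognosis weakens a log-rank test that does not account for the mix, even if azacitidine works equally well in everyone. Separately, a patient with CMML can be eligible and have no named stratum at randomization.

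**Working it through.** **1. Reading the last sentence**

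| Reading | First-remission AML, no listed feature | IPSS floor for MDS |
|---|---|---|
| All earlier conditions are lifted | Eligible | Lifted |
| Only the genetic conditions are lifted | Appears eligible, since lack of adverse genetics no longer excludes | May survive; the sentence does not mention IPSS |
| Only therapy-related disease is meant | Not eligible | Unclear |

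The third reading leaves the words de novo without meaning. So the conflict over first-remission AML stands on every reading that uses all the words; the position for MDS is ambiguous.

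**2. The plan's 214 events**

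Inputs: medians 6 and 9 months, two-sided alpha 0.05, power 0.80, 1:1 allocation. Under exponential RFS the hazard ratio (HR) is 6/9 = 0.667.

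- Fixed design (Schoenfeld): 4 × (1.960 + 0.842)² / (ln 1.5)² = 191 events.
- Stated boundaries at 71/142/214 events, simulated: type I error 0.0499 with futility bounds ignored (0.044 if binding); power 0.801 with futility binding.

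The 214 therefore reproduces.

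**3. When the 214th event falls**

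The documents give no date for it, so it must be derived. Assume uniform accrual of 6 per month to 246 patients (246/6 = 41 months), exponential RFS and no dropout. For an arm with median m, λ = ln 2 / m, and for t ≥ 41

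E(t) = 3 × [41 − (e^(−λ(t−41)) − e^(−λt)) / λ].

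At t = 48.4: control (m = 6) gives 3 × (41 − 3.65) = 112.1, azacitidine (m = 9) gives 3 × (41 − 7.03) = 101.9, total 214. So month 48.4 under the plan's own figures.

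**4. With a share w of lower-risk patients**

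Weight E(t) by 1 − w for medians 6 and 9, and by w for medians m₂ and 1.5 × m₂. The overall control median solves (1 − w) × 2^(−t/6) + w × 2^(−t/m₂) = 0.5. For example, w = 0.2, m₂ = 18, t = 7.2: 0.8 × 0.435 + 0.2 × 0.758 = 0.50. Both w and m₂ are assumptions.

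| Share w | Control median m₂ (months) | Month of 214th event | Overall control median (months) |
|---|---|---|---|
| 0 | – | 48.4 | 6.0 |
| 10% | 12 | 50.1 | 6.4 |
| 20% | 9 | 50.2 | 6.5 |
| 20% | 12 | 51.8 | 6.8 |
| 20% | 18 | 55.0 | 7.2 |
| 40% | 24 | 73.1 | 9.6 |

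**5. Power at 214 events**

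Trials were simulated with 246 patients, HR 0.667 in every patient, analysis at the 214th event and rejection at |Z| > 1.993 (final look only, no interim stopping). The homogeneous case can be checked by hand: Φ(ln 1.5 × √214 / 2 − 1.993) = Φ(2.966 − 1.993) = 0.83. This is the baseline here; the 0.80 in the plan is for the whole sequential procedure.

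| Mixture | Unstratified log-rank | Stratified by risk |
|---|---|---|
| None | 0.83 | – |
| 20% at 12 months | 0.78 | 0.82-0.83 |
| 20% at 18 months | 0.72 | 0.82-0.83 |
| 40% at 24 months | 0.58 (0.60 in separate runs) | 0.82-0.83 |

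In the two mildest mixtures of step 4 the same simulation gave about 0.81 unstratified, so the loss there is small. The mechanism is that higher-risk controls leave the risk set sooner, so the controls still at risk are increasingly lower-risk and the unadjusted contrast shrinks with time.

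**The case against.** Several points on the other side stand.

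- The last sentence sets aside cytogenetics and molecular rearrangements and says nothing of IPSS. A reader might infer that it opens the trial to any MDS and empties the whole criterion. Only the broadest reading supports that.
- A reader might infer that the 6-month median is known to come from high-risk patients and is therefore wrong for a wider intake. The documents name no cohort. It may come from the wider population, and the primary objective is itself worded without the high-risk qualifier. The link is a fair inference from the Preliminaries, not a stated fact.
- A reader might infer that the trial would miss its timeline. The plan states no duration and no month for the final event count; month 48 is derived here.
- The delay depends on inputs that cannot be checked: about 2 months in the mildest mixture shown (50.1 − 48.4 = 1.7) and about 25 in the heaviest (73.1 − 48.4 = 24.7).
- Randomization protects the comparison. Under the null hypothesis both arms have the same mixture, so type I error is not harmed.

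The remaining argument, that an event-driven test keeps its power whatever the population, stands only in part. It holds for a homogeneous population or a test stratified by risk. It does not hold for an unstratified log-rank test on mixed prognosis. The planned covariate-adjusted analyses name no covariate and are not described as the primary test.

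**Conclusion.** The text conflict is real and does not depend on any assumed figure: first-remission AML without a listed feature appears eligible, while the statistical section describes a high-risk population, and CMML has no named stratum. The status of the IPSS floor is unclear.

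The effect on planning is conditional. It arises only if the 6-month figure is a high-risk figure and lower-risk patients enter in some number. The ranges above then show what could follow, from a negligible shift to a serious one. They assume exponential RFS within each risk group, no dropout and the same hazard ratio in every patient; the shares and lower-risk medians are not in the documents. The material does not support the conclusion that the test is invalid or that 214 events is the wrong count for the stated effect. The avoidable weakness is a primary test with no stated allowance for risk in a population whose mix of risk the eligibility text leaves open.

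**What to change.** 1. Reconcile the last sentence of inclusion 1 with the list before it and with the high-risk description in Statistical Considerations, and state whether the IPSS floor applies to the patients it adds. Which population is meant is for the trial team to decide. If the wider one is meant, restate the assumed control median for it and name its source.
2. Record at randomization whether each patient meets the listed high-risk conditions. Stratify the primary log-rank test by that flag, or adjust the primary RFS comparison for it, and report RFS within each level.
3. Assign CMML to a named randomization stratum.

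Cost: wording changes and one yes/no item, which rests on the same facts needed to judge inclusion 1. If the wider population is kept, the planning assumption may become less favourable.

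### Does the symmetric futility bound wrongly keep the trial going when results lean against azacitidine?

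*Combined protocol and SAP*

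**What the plan says.** Under Statistical Considerations, Group sequential design, the plan states: "A two-sided group sequential procedure will be used [2] with overall type I error .05 and power .80 to detect the alternative" of a 9-month median RFS against 6 months. There are up to two interim tests and one final test, "including both outer bounds for superiority and inner bounds for futility". The aim is worded directionally, to "test the hypothesis that azacitidine provides at least a 50% improvement in" median RFS. Under Proposed Treatment/Study Plan the comparator is described thus: "Standard treatment post allogeneic transplant is supportive care only".

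The table gives every cut-off with a plus and a minus sign:

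| Events | Outer | Inner |
|---|---|---|
| 71 | ±3.7103 | ±0.2438 |
| 142 | ±2.5114 | ±1.0268 |
| 214 | ±1.993 | ±1.993 |

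The inner column is headed "Inner Z-score cut-off to accept the null hypothesis (Futility", followed by a closing bracket. The primary objective in the Abstract is non-directional: it compares RFS between the arms and does not mention improvement. Oversight is covered under Data Monitoring Committee ("Does this Protocol need data safety monitoring? Yes"), and the institution's own committee is named.

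**The concern.** Let positive Z favour azacitidine. The rule stops for results close to zero and for results beyond the negative outer bound, but continues between them: from -0.2438 to -3.7103 at look 1 and from -1.0268 to -2.5114 at look 2. As a futility rule for benefit alone this is not monotone, because at look 2 the trial stops at Z = 0 yet continues at Z = -1.03, where the prospect of benefit is far worse.

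The goal is worded as an improvement, power is quoted only for the 9-month alternative, and the columns are labelled superiority and futility. A reader may therefore suspect that one-directional bounds were meant and that the minus signs on the inner column are a slip. If so, patients would continue to be randomised to a drug that could no longer realistically be shown to help.

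**Working it through.** **Inputs.** Looks at 71, 142 and 214 events with the bounds tabulated above; two-sided type I error .05; power .80; medians 6 and 9 months (all from Group sequential design). Randomisation described as fair is read as 1:1. With exponential RFS the design hazard ratio (HR) is 6/9 = 0.667, so the log effect is ln 1.5 = 0.4055. Log-rank information is events/4: 17.75, 35.5 and 53.5.

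**Step 1: reproduce the stated figures.** Recursive numerical integration with the printed bounds gives:

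- Power at HR 0.667 with the inner bounds applied: upper-bound crossings of 0.0226 + 0.4380 + 0.3404 = 0.801, against .80 stated.
- Type I error with the outer bounds alone: 0.0501 (0.0500 at exactly equal information), against .05 stated.
- Type I error if the inner bounds are also enforced: 2 × (0.0001 + 0.0059 + 0.0161) = 0.044, which is below .05.

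The symmetric table therefore delivers what the text claims, and the minus signs are no slip. Type I error reaches .05 only if the outer bounds are two-sided.

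**Step 2: locate the unfavourable zones.** The observed HR at a bound is approximately exp(-2Z/√events).

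- Look 1: Z = -0.2438 gives 1.06; Z = -3.7103 gives 2.41.
- Look 2: Z = -1.0268 gives 1.19; Z = -2.5114 gives 1.52.

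**Step 3: conditional power for benefit at look 2, under HR 0.667.** The formula is 1 - Φ{[1.993√53.5 - Z√35.5 - 0.4055 × 18]/√18}, where 18 = 53.5 - 35.5.

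- Z = 0: (14.578 - 7.298)/4.243 = 1.716, giving 0.043. The trial stops.
- Z = -1.0268: (14.578 + 6.118 - 7.298)/4.243 = 3.158, giving 0.0008. The trial continues.
- Z = +1.0268: (14.578 - 6.118 - 7.298)/4.243 = 0.274, giving 0.39. The trial continues.

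By symmetry, at Z = -1.0268 the conditional power to show azacitidine worse, under HR 1.5, is also 0.39. At Z = 0 it is 0.043 in either direction. For a two-sided question the rule is therefore coherent: it stops where neither conclusion is likely and continues where one of them still is.

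**Step 4: price the alternative.** Compare the printed rule with a rule that uses the same inner cut-offs in the direction of benefit only. Expected events are Σ(stopping probability × events).

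- HR 1.0, printed: 71 × 0.1929 + 142 × 0.5436 + 214 × 0.2635 = 147.
- HR 1.0, one-directional: 71 × 0.5964 + 142 × 0.2778 + 214 × 0.1258 = 109.

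| Quantity | Printed | One-directional at both looks | One-directional at look 2 only |
|---|---|---|---|
| Power for benefit, HR 0.667 | 0.801 | 0.795 | 0.801 |
| Expected events, HR 1.0 | 147 | 109 | 138 |
| Expected events, HR 1.25 | 167 | 80 | 134 |
| Probability of showing harm, HR 1.5 | 0.80 | 0.02 | 0.46 |

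The harm row keeps the negative outer bound at any look where it is still reachable. With both looks changed, rejection under the null falls from about 0.044 to about 0.022, so the declared two-sided .05 test becomes in effect a one-sided test at about .022.

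**The case for a change.** The strongest case for the concern is look 2. Continuing in the lower zone there can in practice serve only to show that azacitidine is worse, and the plan never names that as an aim. The zone is not rare: under the printed rule the trial continues past look 2 with negative Z 13% of the time at HR 1.0 and 46% at HR 1.25. Making only look 2 one-directional costs no detectable power for benefit. Two-sided efficacy bounds do not force a symmetric futility bound. The plan also does not say whether the inner bound is binding.

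These facts are correct, but they do not amount to a defect:

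- **Aim.** A two-sided test with a negative rejection bound already makes a finding of inferiority a planned outcome, and the neutral primary objective agrees with it. The directional sentence sets the effect size for power.
- **Harm rule and sign.** The negative outer bound is itself a formal RFS harm boundary. The unstated sign convention changes nothing while the bounds are symmetric.
- **Look 1.** Near the inner edge, at Z = -0.24, benefit is still within reach: conditional power is 0.34 with the look-2 wedge enforced and 0.43 ignoring look 2. Yet much of the apparent saving comes from look 1: at HR 1.25, changing both looks saves 167 - 80 = 87 events, and changing look 2 alone saves 167 - 134 = 33.
- **Exposure.** About 193 of 246 patients would already be enrolled at look 2 under HR 1.0, leaving at most 53. This assumes 6 patients a month, a control median of 6 months, exponential RFS, no dropout and no pause in enrolment. The HR of 1.25 is an assumed scenario, not one in the plan.
- **Cost.** Even the look-2-only change lowers the probability of showing harm at HR 1.5 from 0.80 to 0.46. An active drug is being given to patients already in post-transplant remission, against supportive care, so firm evidence of worse RFS has evident value.

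What stands is a wish for a sentence on why the wedge was chosen and whether it binds the monitoring committee. That would help the reader, but the results are sound without it.

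**Conclusion.** The concern does not hold. The plan declares a two-sided procedure, prints two-sided bounds, and gets from them the power (0.801) and type I error (0.050 from the outer bounds, 0.044 with the inner bounds enforced) that it states. Continuing in the intermediate zone on the unfavourable side is the intended behaviour of that design.

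A one-directional futility rule is a legitimate alternative. It saves 147 - 109 = 38 expected events under the null and costs 0.6 points of power for benefit, but it nearly abolishes the ability to show harm at HR 1.5 (0.80 to 0.02). Choosing between the two is a matter of preference.

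The figures assume 1:1 allocation, proportional hazards with HR 0.667 as the alternative, and looks triggered by events as in Group sequential design. The Data Monitoring Committee section instead ties the looks to 71 and 142 patients accrued. That is a separate matter and does not bear on whether symmetric bounds are proper.

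### The final analysis has two conflicting triggers (214 events, or completion of enrollment at up to 246 patients), and no rule covers a final count below 214

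*Combined protocol and SAP*

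**What the plan says.** Under Statistical Considerations, Group sequential design: "The primary outcome for treatment evaluation will be relapse-free survival (RFS) time". The control assumption follows: "A null historical RFS time of 6 months will be assumed", and the target is an improvement in "median RFS, from 6 to 9 months", planned "with overall type I error .05 and power .80 to detect the alternative" of 9 months. The table gives two interim looks and one final look, at 71, 142 and 214 events. The final cut-off is ±1.993, and no other final event count has a boundary. On size: "The number of patients accrued (sample size) required to achieve the necessary numbers of events required by the group sequential tests will be between 213" (the upper figure is 246). The Estimated Accrual section fixes the maximum: "Total Accrual at MDACC: 246", at 6 patients per month.

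The Data Monitoring Committee section describes the same looks differently. It places the interims at 71 and 142 patients accrued and the final analysis at completion of enrollment, and refers back to the statistical section.

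Two further statements bear on the shape of the RFS curve. The Rationale says that "the major cause of failure is disease relapse, which usually occurs early after transplantation". Inclusion criterion 3 reads "Patients must be in complete remission post transplant", and criterion 4 allows entry 40 to 100 days after transplant.

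**The concern.** The table counts events and the Data Monitoring Committee section counts patients. The two cannot both govern the final look unless nearly everyone has had an event by the day the last patient enters.

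Each reading has its own weakness. If completion of enrollment governs, the final test comes with fewer events than the design needs. If 214 events govern, the target needs an 87% event rate, with no time limit and no rule for falling short. Early relapse, and entry restricted to patients in remission some weeks after transplant, both suggest a hazard that falls with follow-up, whereas the sizing is reproduced by a constant hazard.

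The treatment is unblinded and all patients are enrolled at one centre. If the event count stalls below 214, the analysis date would have to be chosen when results may already be visible.

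**Working it through.** **Inputs.** Group sequential design: 71/142/214 events; outer cut-offs 3.7103, 2.5114, 1.993; inner cut-offs 0.2438, 1.0268, 1.993; medians 6 and 9 months; 6 patients per month; 1:1 allocation (my reading of fair randomization). Estimated Accrual: 246 patients.

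**1. The plan's own figure.** With exponential RFS the hazard ratio is 6/9 = 0.667, so the drift is ln 1.5. Taking information as events/4 and integrating over the printed boundaries:

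- Power at 214 events, binding futility: 0.023 + 0.438 + 0.340 = 0.801. The stated 0.80 reproduces.
- Two-sided type I error: 0.050 with futility ignored, 0.044 with futility binding.
- Probability of needing the third look: 0.43 under the alternative, 0.26 under the null. Hence 57% and 74% of trials stop by the second look. The third look supplies 0.34 of the 0.80 power.

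**2. Final analysis at completion of enrollment.** Accrual lasts 246/6 = 41 months. Each arm accrues 3 patients per month, so expected events per arm at month t during accrual are 3 × [t − (1 − e^(−λt))/λ], with λ = ln 2/median. At t = 41:

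- Median 6: 3 × (41 − 8.58) = 97.3
- Median 9: 3 × (41 − 12.43) = 85.7
- 6 vs 9: about 183 events. 6 vs 6: about 195 events.

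Both are short of 214 with no plateau at all. Keeping the event-based interims and the printed 1.993, power at 183 final events is 0.756.

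The interims differ too. The same formula at t = 71/6 and t = 142/6 months (6 vs 9) gives about 28 and 85 events, not 71 and 142.

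**3. Final analysis at 214 events.** With constant hazard and 246 patients, 214 events arrive at month 45.1 (6 vs 6) or 48.4 (6 vs 9), which is 4 to 7 months after accrual ends.

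The largest share without an observed event that still allows 214 is 1 − 214/246 = 13.0%. With a common plateau p, the most events possible is 246(1 − p). Time to 214 events is from a mixture model with medians held at 6 and 9 months:

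| Common plateau p (assumed) | Most events in 246 | 214 events reached after end of accrual |
|---|---|---|
| 5% | 234 | about 11 months |
| 10% | 221 | about 18 months |
| 12% | 216 | about 28 months |
| 15% | 209 | never |
| 20% | 197 | never |
| 30% | 172 | never |

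If the hazard ratio stays at 2/3 throughout, a control plateau p implies p^(2/3) on azacitidine, and the most events is 123(1 − p) + 123(1 − p^(2/3)). Control plateaus of 5, 10, 15, 20 and 30% give 223, 207, 193, 179 and 154. Setting the expression to 214 requires p + p^(2/3) = 32/123 = 0.260, so p is about 8%.

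**4. A final test with fewer events.** Interims at 71 and 142 events, final cut-off kept at 1.993:

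| Final events | Power (binding futility) | Two-sided type I error (futility ignored) |
|---|---|---|
| 214 | 0.80 | 0.050 |
| 190 | 0.77 | 0.049 |
| 180 | 0.75 | 0.048 |
| 160 | 0.71 | 0.047 |

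**The case against.** A reader might infer that the final test is never reached, or that the trial could end with no valid final test. The documents do not support either.

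- The Data Monitoring Committee section does provide for a final analysis, at completion of enrollment. That stands, but it does not settle the matter. The sentence defers to the statistical section, whose only final boundary is at 214 events, and about 183 to 195 are expected by then.
- On the plan's own model 214 events are feasible within months of the last enrollment. A plateau above 13% is an assumption. The Rationale and the remission criterion suggest a falling hazard but fix no plateau of any size, and the Rationale also speaks of high failure rates.
- The printed 1.993, used at a lower prespecified count, keeps two-sided type I error at or below about 0.05. The exposure is therefore lost power and an unspecified analysis date, not an inflated boundary.
- The primary question may be settled at an interim. The 142-event look remains reachable even with a 40% plateau, where 246 × 0.60 = 148 events are possible.

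A reader might also infer that the lower figure of 213 patients is simply impossible beside 214 events. It is if 213 is meant for the final look. But the sentence covers all the tests, and on the plan's accrual rate about 193 to 215 patients would be enrolled when 142 events occur (medians 6/6 to 9/9). So 213 may describe an early stop. The text is unclear rather than proven wrong.

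**Conclusion.** The point holds as a conflict between two triggers together with a missing shortfall rule. Read by enrollment, the final look has about 183 events at the alternative and power of about 0.75 to 0.76 instead of 0.80. This assumes exponential RFS, 6 patients per month, no loss to follow-up, and interims still taken at 71 and 142 events. Read by events, the target is attainable under constant hazard but has limited slack: it fails once more than 13% of the 246 patients have no observed RFS event, counting those lost to follow-up. At a constant hazard ratio of 2/3, a control plateau of roughly 8% is enough. Whether such a plateau exists cannot be judged from the documents. The matter is worth correcting because the third look carries 0.34 of the 0.80 power and is needed in 43% of trials under the alternative. It does not show that the trial's primary test is invalid.

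**What to change.** - Reconcile the Data Monitoring Committee section with the group sequential table so that all three looks are triggered by RFS events.
- State that the final analysis takes place at 214 RFS events or a fixed time after the last randomization (for example 24 months), whichever comes first.
- Set the final critical value for the actual event count by error spending. Keeping 1.993 would be slightly conservative.
- State the power for a shortfall: about 0.77 at 190 events, 0.75 at 180 and 0.71 at 160.
- Say what the lower figure of 213 patients refers to, and correct it if it is meant for the final look.

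The cost is about a paragraph in the statistical section and a matching edit to the monitoring section, with no extra patients. The downside is a slightly lower stated power if the time limit comes first.
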